Survival status: phone contact with subjects who refuse to return for evaluations and agree to be contacted		X	X	X	X	X	X	X (every 2 months)
Hematology ^c	X	X	X					
Chemistry ^d	X	X	X					
Thyroid function tests (TSH, and fT3 and fT4) ^e	X							

Evaluation	Time Since Last Dose of Durvalumab or Tremelimumab or Olaparib							
	Day (± 3)	Months (± 1 week)						12 Months and Every 6 Months (± 2 weeks)
	30	2	3	4	6	8	10	
Tumour assessment (CT or MRI)	
For subjects who achieve disease control following 12 months of treatment, tumour assessments should be performed every 12 weeks relative to the date of first infusion thereafter until confirmed PD by irRECIST by investigational site review. Please refer to Table 5 for timings of confirmatory scans.
 
For subjects who discontinue durvalumab + tremelimumab due to toxicity (or symptomatic deterioration), tumour assessments should be performed relative to the date of first infusion as follows: every 12 weeks until confirmed PD by irRECIST by investigational site review or started on standard therapy or another clinical study. Please refer to Table 5 for timings of confirmatory scans.
 
Upon confirmed PD or initiation of standard therapy, scans should be conducted according to local standard clinical practice.
							

- a Full physical exam (refer to Section 8.3.2).
- b Refer to Section 8.3.4.
- c Refer to Section 8.3.5, Table 6..
- d Refer to Section 8.3.5, Table 7.
- c Free T3 and free T4 will only be measured if TSH is abnormal. They should also be measured if there is clinical suspicion of an adverse event related to the endocrine system.

Appendix I Schedule of study procedures: follow-up for subjects who have discontinued study treatment due to confirmed progression of disease at the investigator discretion

Evaluation	Time Since Last Dose of Durvalumab or Tremelimumab or Olaparib						
	Day (± 3)	Months (± 1 week)					
	30	2	3	4	6	8	10
Physical examination ^a	X						
Vital signs (temperature, respiratory rate, blood pressure, pulse) ^b	X						
Weight	X						
AE/SAE assessment	X	X	X				
Concomitant medications	X						
Palliative radiotherapy	As clinically indicated						
ECOG performance status ^c	X					→	
Subsequent anti-cancer therapy	X	X	X	X	X	X	X
Survival status: phone contact with subjects who refuse to return for evaluations and agree to be contacted		X	X	X	X	X	X (every 2 months)
Hematology ^d	X						
Chemistry ^e	X						
Thyroid function tests (TSH, and fT3 and fT4) ^f	X						
miRNA/mRNA (to examine immune cell gene expression profiles in circulation), if applicable	X						
blood for immune monitoring	X						
Tumour assessment (CT or MRI)	For subjects who continue on durvalumab + tremelimumab post-confirmed progression at the investigator's discretion (following consultation with the sponsor), tumour assessments should be performed relative to the date of first infusion per Table 5 until durvalumab + tremelimumab is stopped. For subjects who discontinue durvalumab + tremelimumab following confirmed progression , scans should be conducted according to local clinical practice and submitted for central review until a new treatment is started (these scans are optional).						

a Full physical exam (refer to Section 8.3.2)

b Refer to Section 8.3.4.

c Refer to Section 8.3.4, Table 6.

d Refer to Section 8.3.4, Table 7.

e PS to be collected if available at the 2 monthly calls to obtain subsequent anti-cancer therapy and survival status

f Free T3 and free T4 will only be measured if TSH is abnormal. They should also be measured if there is clinical suspicion of an adverse event related to the endocrine system.

Appendix J Diary for Medication (Olaparib)

Study No.: _____

Patient Name: _____

Drug Name: _____

Cycle (Please circle one.): 1 2 3 4 5 6
 7 8 9 10 11 12

Medical Record No.: _____

Study Medication Calendar

Please complete this calendar on a daily basis immediately after you take your pills. Fill in the date for each day and the time the pill is taken in the AM and PM space (not check mark) and write the total number of pills you take each day.

Start Date: _____

Cycle Day		Day 1	Day 2	Day 3	Day 4	Day 5	Day 6	Day 7
Date								
Dose								
Number of pills taken (Please Note time)	AM							
	PM							

Cycle Day		Day 8	Day 9	Day 10	Day 11	Day 12	Day 13	Day 14
Date								
Dose								
Number of pills taken (Please Note time)	AM							
	PM							

Cycle Day		Day 15	Day 16	Day 17	Day 18	Day 19	Day 20	Day 21
Date								
Dose								
Number of pills taken (Please Note time)	AM							
	PM							

Cycle Day		Day 22	Day 23	Day 24	Day 25	Day 26	Day 27	Day 28
Date								
Dose								
Number of pills taken (Please Note time)	AM							
	PM							

Please remember to bring this calendar and your pill bottle (including any unused pills) with you to your next clinic appointment.

Roswell Park Protocol No.: I 288216

Coordinator's Use Only

$$\% \text{ Compliance} = \left(\frac{\text{Number of Pills Dispensed} - \text{Number of Pills Returned}}{\text{Number of Pills Scheduled}} \right) \times 100$$

$$\text{____ \% Compliance} = \left(\text{_____} - \text{_____} \right) \times 100$$

Patient signature: _____

Date: _____

CRC signature: _____

Date: _____

Investigator signature: _____

Appendix K irRECIST Summary

Tumor response assessment using the Immune-Related response Criteria as described by Nishino et al, 2013* and Bohnsack et al, 2014**.

1.0 Baseline

1.1 Measurable Lesion Definitions and Target Lesion Selection

- All measurable lesions up to a maximum of 2 lesions per organ and 5 lesions in total, representative of all involved organs, will be identified as target lesions and recorded and measured at baseline
- Measurable lesions must be accurately measured in at least one dimension with a minimum size of:
 - 10 mm in the longest diameter by CT or MRI scan (or no less than double the slice thickness) for non- nodal lesions and ≥ 15 mm in short axis for nodal lesions.
 - 10 mm caliper measurement by clinical exam (lesions which cannot be accurately measured with calipers should be recorded as non-measurable).
 - 20 mm by chest X-ray
- A sum of the longest diameter (short axis for lymph nodes) of all target lesions will be calculated and reported as the baseline sum diameters. This will be used as reference to further characterize the objective tumor response of the measurable dimension of the disease.

1.2 Non-measurable Lesion Definitions

- Non-target lesions will include:
 - Measurable lesions not selected as target lesions
 - All sites of non-measurable disease, such as neoplastic masses that are too small to measure because their longest uninterrupted diameter is < 10 mm (or $<$ two times the axial slice thickness), i.e., the longest perpendicular diameter is ≥ 10 and < 15 mm.
 - Other types of lesions that are confidently felt to represent neoplastic tissue, but are difficult to measure in a reproducible manner. These include bone metastases, leptomeningeal metastases, malignant ascites, pleural or pericardial effusions, ascites, inflammatory breast disease, lymphangitis cutis/pulmonis, cystic lesions, ill-defined abdominal masses, skin lesions, etc.
- All lesions or sites of disease not recorded as target lesions (e.g., small lesions and non-measurable lesions) should be identified as non-target lesions and indicated as present in the source documents at baseline. There is no limit to the number of non-target lesions that can be recorded at baseline. The general location will also be documented on the images, drawing a regularly-shaped Region of Interest.
- Measurements of the non-target lesions will not be performed, but the presence or absence of each should be noted throughout follow-up and evaluation.

1.3 Target and Non-Target Lymph Node Lesion Definitions

- To be considered pathologically enlarged and measurable, a lymph node must be ≥ 15 mm in short axis when assessed by CT scan (CT scan slice thickness recommended to be no greater than 5 mm). At baseline and in follow-up, only the short axis will be measured and followed.

1.4 Non-Target Lesion Selection

- All lesions or sites of disease not recorded as target lesions should be recorded as non-target lesions at baseline. There is no limit to the number on non-target lesions that can be recorded at baseline.

1.5 Bone Lesions

- Bone scan, PET scan or plain films are not considered adequate imaging techniques to measure bone lesions. However, these techniques can be used to confirm the presence or disappearance of bone lesions.
- Regardless of the imaging modality blastic bone lesions will not be selected as target lesions. Lytic or mixed lytic-blastic lesions with a measurable soft tissue component ≥ 10 mm can be selected as target lesions.

1.6 Brain Lesions

- Brain Lesions detected on brain scans can be considered as both target or non-target lesions.

1.7 Cystic and Necrotic Lesions as Target Lesions

- Lesions that meet the criteria for radiographically defined simple cysts should not be considered as malignant lesions (neither measurable nor non-measurable) since they are, by definition, simple cysts.
- Lesions that are partially cystic or necrotic can be selected as target lesions.
- The longest diameter of such a lesion will be added to the ***Total Measured Tumor Burden (TMTB)***¹ of all target lesions at baseline.
- If other lesions with a non-liquid/non-necrotic component are present, those should be preferred.

1.8 Lesions with Prior Local Treatment

- During target lesion selection the radiologist will consider information on the anatomical sites of previous intervention (e.g. previous irradiation, RF-ablation, TACE, surgery, etc.).
- Lesions undergoing prior intervention will not be selected as target lesions unless there has been a demonstration of progress in the lesion.

1.9 No Disease at Baseline

- If a patient has no measurable and no non-measurable disease at baseline the radiologist will assign ‘**No Disease**’ (irND) as the overall tumor assessment for any available follow-up time-points unless new measurable lesions are identified and contribute to the TMTB.

2.0 Follow-Up

2.1 Recording of Target and New Measurable Lesion Measurements

- The longest diameters of non-nodal target and new non-nodal measurable lesions, and short axes of nodal target and new nodal measurable lesions will be recorded. Together they determine the ***Total Measured Tumor Burden (TMTB)*** at follow-up.

$$\text{TMTB \% change} = \frac{\text{Baseline Tumor Burden} - \text{Current Tumor Burden}}{\text{Baseline Tumor Burden}} \times 100$$

2.1 Definition of New Measurable Lesions

- In order to be selected as new measurable lesions (≤ 2 lesions per organ, ≤ 5 lesions total, per time-point), new lesions must meet criteria as defined for baseline target lesion selection and meet the same minimum size requirements of 10 mm in long diameter and minimum 15 mm in short axis for new measurable lymph nodes. New measurable lesions shall be prioritized according to size, and the largest lesions shall be selected as new measured lesions.

2.2 Non-Target Lesion Assessment

- The RECIST 1.1 definitions for the assessment of non-target lesions apply (i.e., measurements of the non-target lesions will not be performed, but the presence or absence of each should be noted throughout follow-up and evaluation).
- The response of non-target lesions primarily contributes to the overall response assessments of irCR and irNon-CR/Non-PD (irNN).
- Non-target lesions do not affect irPR and irSD assessments.
- Only a massive and unequivocal worsening of non-target lesions alone, even without progress in the TMTB is indicative of irPD.

2.3 New Non-Measurable Lesions Definition and Assessment

- All new lesions not selected as new measurable lesions are considered new non-measurable lesions and are followed qualitatively.
- Only a massive and unequivocal progression of new non-measurable lesions leads to an overall assessment of irPD for the time-point.
- Persisting new non- measurable lesions prevent irCR.

2.4 irRECIST Overall Tumor Assessments

The irRECIST overall tumor assessment is based on the **TMTB** (total measured tumor burden) of measured target and new lesions, non-target lesion assessment and new non-measurable lesions.

Time point response assessments will be performed on Cycle 4 Day 1 (± 7 days) and then every 3 cycles.

Conventional RECIST 1.1 will also be documented during the trial however; RECIST 1.1 will not be used to determine disease progression. The irRECIST will be used for tumor response assessment at time of continuing review and will be used for IRB reporting and formal analysis.

- **irCR:** Complete disappearance of all measurable and non-measurable lesions. Lymph nodes must decrease to < 10 mm in short axis. Confirmation of response is not mandatory.
- **irPR:** Decrease of $\geq 30\%$ in TMTB relative to baseline, non-target lesions are irNN, and no unequivocal progression of new non-measurable lesions.
- **irSD:** Failure to meet criteria for irCR or irPR in the absence of irPD.

- **irNN:** No target disease was identified at baseline and at follow-up the patient fails to meet criteria for irCR or irPD.
- **irPD:** Minimum 20% increase and minimum 5 mm absolute increase in TMTB compared to nadir, or irPD for non-target or new non-measurable lesions. Confirmation of progression is recommended minimum 4 weeks after the first irPD assessment.
- **irNE:** Used in exceptional cases where insufficient data exists.
- **irND:** In adjuvant setting when no disease is detected.

New Lesions: the presence of new lesion(s) does not define progression. The measurements of the new lesion(s) are included in the sum of the measurements (the sum of the measurements = the sum of the longest diameters of all target lesions and new lesions, if any).

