2. All patients must have measurable disease as defined by irRECIST. Measurable disease is defined as 10 mm in the longest diameter by CT or MRI scan (or no less than double the slice thickness) for non- nodal lesions and ≥ 15 mm in short axis for nodal lesions, 20 mm by chest X-ray, a lymph node must be ≥ 15 mm in short axis when assessed by CT scan (CT scan slice thickness recommended to be no greater than 5 mm).
3. Must have archival tissue available for PD-L1 assessment.
4. Patients should be free of active infection requiring antibiotics (with the exception of uncomplicated UTI).

5. Patients who have the following risk factors are considered to be at increased risk for cardiac toxicities and may be enrolled only with increased monitoring (refer to Table 5, footnote 5): i) prior treatment with anthracyclines, ii) prior treatment with trastuzumab, iii) a New York Heart Association classification of II controlled with treatment, iv) prior central thoracic radiation therapy (RT), including RT to the heart.
6. Any hormonal therapy being taken as a treatment for cancer must be discontinued at least one week prior to registration. Continuation of hormone replacement therapy e.g. thyroid hormone replacement therapy is permitted.
7. Able to tolerate oral medications and no GI illnesses that would preclude absorption of olaparib.
8. Female patients, age \geq 18 years at time of study entry.
9. Have an ECOG Performance Status of 0-1. Refer to Appendix B.
10. Life expectancy of $>$ 6 months.
11. Adequate normal organ and marrow function as defined below:
 - o Hemoglobin \geq 10 g/dL (no blood transfusion in the 28 days prior to entry (olaparib guidelines))
 - o WBC $>$ 3 \times 10⁹/L
 - o Absolute neutrophil count (ANC) \geq 1.5 \times 10⁹/L (\geq 1500 per mm³)
 - o Platelet count \geq 100 \times 10⁹/L (\geq 100,000 per mm³)
 - o Serum bilirubin \leq 1.5 \times institutional upper limit of normal (ULN). This will not apply to subjects with confirmed Gilbert's syndrome (persistent or recurrent hyperbilirubinemia that is predominantly unconjugated in the absence of hemolysis or hepatic pathology), who will be allowed only in consultation with their physician
 - o AST (SGOT)/ALT (SGPT) \leq 2.5 \times institutional upper limit of normal unless liver metastases are present, in which case it must be \leq 5x ULN
 - o Creatinine \leq 1.5 \times ULN or, Serum Creatinine CL $>$ 51 mL/min (by the Cockcroft-Gault equation: see Appendix L).

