8.5.1.2 Fresh tumor biopsies

Tumor lesions planned for biopsy must not be used as index lesions for assessment of disease and tumor response. Excisional biopsies are preferred where clinically appropriate. Otherwise, subjects will undergo 4 image-guided core biopsies (18 g or larger, if clinically appropriate). Two tissue cores will be placed in formalin and processed to FFPE. The remaining 2 cores will be immediately frozen in liquid nitrogen and then stored at -80°C. Network sites will ship the samples in formalin at room temperature on the same day as collection to the central lab (IAF) as per lab manual. Flash frozen samples can be batch shipped to the Central Lab on dry ice.

Additional details for sample collection, processing, storage, and shipment is provided in the ***Laboratory Manual [RPCI Immune Analysis Facility study Laboratory Manual (Version 2.0)]***.

Tumor biopsy will be performed on Cycle 4 Day 1 ± 7 days (if clinically appropriate), or at time of progression (if clinically appropriate). Archived sample will be utilized for baseline assessment.

Note: All investigator or analyzing research laboratories housing research samples need to maintain current **Temperature Logs** and study-specific **Sample Tracking and Shipping Logs**. The Principal Investigator/Laboratory Manager **must** ensure that the stated lab(s) have a process in place to document the receipt/processing/storage/shipping of study-related samples/specimens. This is required for both observational and interventional clinical studies collecting clinical samples.

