9 EFFICACY EVALUATIONS

Disease Evaluation and Methods

The response to immunotherapy may differ from the typical responses observed with cytotoxic chemotherapy, including the following (50, 51):

- Response to immunotherapy may be delayed
- Response to immunotherapy may occur after PD by conventional criteria
- The appearance of new lesions may not represent PD with immunotherapy
- SD while on immunotherapy may be durable and represent clinical benefit.

Based on the above-described unique response to immunotherapy and based on guidelines from regulatory agencies, e.g., European Medicines Agency's "Guideline on the evaluation of anti-cancer medicinal products in man" (52) for immune modulating anti-cancer compounds, the study may wish to implement the following in addition to standard RECIST 1.1 criteria (53):

- RECIST will be modified so that PD must be confirmed at the next scheduled visit, preferably, and no earlier than 4 weeks after the initial assessment of PD in the absence of clinically significant deterioration. Treatment with durvalumab, tremelimumab, and olaparib would continue between the initial assessment of progression and confirmation for progression.
- In addition, subjects may continue to receive durvalumab, tremelimumab, and olaparib beyond confirmed PD in the absence of clinically significant deterioration and if investigators consider that subjects continue to receive benefit from treatment.

Modification of RECIST as described may discourage the early discontinuation of durvalumab/olaparib and provide a more complete evaluation of its anti-tumor activity than would be seen with conventional response criteria. Nonetheless, the efficacy analysis will be conducted by programmatically deriving each efficacy endpoint based on RECIST 1.1 criteria.

Of note, clinically significant deterioration is considered to be a rapid tumor progression that necessitates treatment with anti-cancer therapy other than durvalumab/olaparib or with symptomatic progression that requires urgent medical intervention (e.g., central nervous system metastasis, respiratory failure due to tumor compression, spinal cord compression).

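### Appendix K contradicts itself on whether non-target lesions affect irPR, and as worded can score a partial responder as stable disease

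*Combined protocol and SAP*

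**What the plan says.** Appendix K (irRECIST Summary) of the combined protocol and SAP addresses this in three places.

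- **Appendix K 2.4, irPR.** The patient needs a decrease of at least 30% "in TMTB relative to baseline, non-target lesions are irNN, and no unequivocal progression of new non-measurable lesions".
- **Appendix K 2.2, non-target lesions.** "Non-target lesions do not affect irPR and irSD assessments". The same list says: "The response of non-target lesions primarily contributes to the overall response assessments of irCR and irNon-CR/Non-PD (irNN". Here irNN abbreviates non-CR/non-PD.
- **Appendix K 2.4, irNN.** "No target disease was identified at baseline and at follow-up the patient fails to meet criteria for irCR or irPD". Here irNN is an overall category for a patient.

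In 2.4, irSD is what remains when irCR, irPR and irPD are all not met. irPD is a rise from nadir of at least 20% and at least 5 mm in total measured tumor burden (TMTB), or irPD in non-target or new non-measurable lesions. The only printed percent-change formula, in the first of the two subsections numbered 2.1, is (baseline − current)/baseline × 100.

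Appendix K 2.4 makes irRECIST the basis for formal analysis. Section 12.4 summarizes tumor response by irRECIST and RECIST descriptively.

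**The concern.** A response category should follow from one rule. Here 2.2 removes non-target lesions from the irPR decision and 2.4 puts them back as a required condition, so two people applying Appendix K to the same scans can reach different categories. The condition in 2.4 also runs the wrong way for some patients: complete disappearance of non-target disease is better than persistence, yet only persistence satisfies non-CR/non-PD. At stake is the irRECIST response rate, which could be too low or could depend on which subsection was followed.

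**Working it through.** **The plan's own figure.** Section 12.4 states power 0.72 for N = 27 (18 platinum-resistant, 9 platinum-sensitive) at α = 0.10, with rates of 0.55 against 0.75 and 0.65 against 0.80. Let R be the sum of Bin(18, p₁) and Bin(9, p₂). Rejecting for R ≥ 20 gives exact α = 0.0682 and power 0.7172, which rounds to 0.72. Rejecting for R ≥ 19 would give α = 0.1399, above 0.10. The figure is reproduced, and it does not depend on how irPR is defined.

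**Applying the irPR rule.** Take an illustrative patient with TMTB 60 mm at baseline, now 30 mm, and no new lesions. The decrease is (60 − 30)/60 = 50%, so the size criterion is met. Targets remain, so irCR is not met. The category then depends on the non-target lesions and on which text is followed:

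| Non-target lesions | Following 2.2 | Following 2.4, irNN = non-CR/non-PD | Following 2.4, irNN = no target disease at baseline |
|---|---|---|---|
| Persist, not progressed | irPR | irPR | irSD |
| All disappeared | irPR | irSD | irSD |
| None at baseline | irPR | irSD as worded | irSD |
| Massive, unequivocal worsening | irPD | irPD | irPD |

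The second row shows the fault most clearly. The same 50% shrinkage is irPR if non-target disease persists and irSD if it has vanished. In the third row there are no non-target lesions to be non-CR/non-PD. A reader could treat the condition as met by default, but Appendix K does not say so.

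**Size per patient.** If all Phase II patients are in the denominator, one patient moved from irPR to irSD lowers the response rate by:

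- overall: 1/27 = 3.7 percentage points
- platinum-resistant stratum: 1/18 = 5.6 percentage points
- platinum-sensitive stratum: 1/9 = 11.1 percentage points

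Section 12.4 limits efficacy to patients with two cycles and a post-baseline assessment. The denominators may therefore be smaller and each step larger.

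**The percent-change formula.** With illustrative values in mm:

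- 100 to 70: the formula gives (100 − 70)/100 = +30%, which meets a threshold worded as a decrease of at least 30%.
- 100 to 120: it gives −20%, which is a 20% increase.
- 100, then nadir 60, then 75: it gives (100 − 75)/100 = +25%, a net decrease from baseline. From nadir the change is (75 − 60)/60 = +25% and +15 mm, which is irPD under the wording of 2.4.

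The formula is thus a percent decrease from baseline carrying a percent-change label. It is not a tool for irPD, and 2.4 does not tell anyone to use it for that.

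**The case against.** The strongest reply is that this is a wording slip in a descriptive summary. Section 2.2 expands irNN as non-CR/non-PD, the irPR line applies the term to lesions, and an experienced reader would choose that sense and award irPR when non-target disease has gone. The choice of sense is sound. The last step, however, sets aside the wording of 2.4 in favour of 2.2, and the plan does not say which governs.

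The reply does defeat several stronger readings that a reader might infer:

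- **That no enrolled patient could ever be irPR.** This takes irNN in its patient-level sense and joins it to Inclusion Criterion 2: "All patients must have measurable disease as defined by irRECIST". The documents do not force that sense, because 2.2 supplies one that enrolled patients can have. Even the patient-level category is not strictly closed to them, since some measurable lesions may not serve as targets. Appendix K 1.8 says "Lesions undergoing prior intervention will not be selected as target lesions unless there has been a demonstration of progress in the lesion", and Section 8.5.1.2 says "Tumor lesions planned for biopsy must not be used as index lesions for assessment of disease and tumor response".
- **That progression is misderived.** The irPD line names the nadir, the 20% and the 5 mm. The formula would mislead only someone who programmed it alone and ignored that line. Its sign changes no threshold, because the thresholds are worded as a decrease and an increase.
- **That Section 9 commits the sponsor to programming these rules.** The sentence containing "the efficacy analysis will be conducted by programmatically deriving each efficacy endpoint" goes on to name RECIST 1.1, so it is not evidence about Appendix K's irRECIST categories. The support comes from 2.4, which assigns irRECIST to formal analysis.

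**Conclusion.** The point holds for the irPR definition. Appendix K 2.2 and 2.4 cannot both be applied, and the wording of 2.4 withholds irPR from some patients with at least 30% shrinkage under either sense of irNN. The irRECIST response rate can be understated by 3.7 percentage points overall for each such patient, with all 27 Phase II patients in the denominator. How many there will be cannot be judged from the documents. The conclusion for patients without any non-target lesions also assumes that an empty condition is not counted as met.

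It would be wrong to carry this over to the primary endpoint. The 3-month and 6-month rates in Section 12.4 turn on progression, and a patient moved between irPR and irSD is progression-free either way. The 0.72 power stands. The formula is a labelling matter only.

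**What to change.** In Appendix K 2.4, define irPR as a decrease of at least 30% in TMTB from baseline, with no irPD in non-target lesions and with new non-measurable lesions not having unequivocally progressed. Delete the requirement that non-target lesions be irNN. Reword 2.2 to match: non-target lesions do not enter irPR or irSD unless they amount to irPD. Keep irNN for the patient-level category only, and write non-CR/non-PD where the lesion-level status is meant.

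As a minor companion edit, relabel the formula in Appendix K 2.1 as percent decrease from baseline. Beside it, state that irPD uses (current − nadir)/nadir × 100 together with the absolute change in mm, as 2.4 already says in words.

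The cost is a few lines of Appendix K and the matching lines of any programming specification. No additional scans or data are needed, and neither the sample size nor the primary test changes.
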